#### After randomisation:

For both treatment arms, post randomisation CT scans of thorax and upper abdomen will be repeated according to the schedule indicated below, until tumour progression:

- up to 18 months: every 9 weeks 9, 18, 27, 36, 45, 54, 63, 72, 81 (+/- 1 week)
- up to 2 years: every 12 weeks 93, 105 (+/- 1 week)
- years 3 and 4: every 6 months (26 weeks) 131, 157, 183, 209 (+/- 1 week)
- at 5 years: 260 (+/- 1 week)

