## 14. Endpoints definition

### 14.1. Progression-free survival

It is defined as the time from the date of randomisation until documented progression or death, if progression is not documented. Censoring will occur at the last tumour assessment only if patient is lost to follow-up.

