### **19.2. Discontinuation of protocol treatment for individual patients**

Protocol treatment should be stopped in the following situations:

- Disease progression.

- Occurrence of unacceptable toxicities. Stopping protocol treatment is determined by medical judgment of the treating physician.
- Inter-current severe illnesses which would in the judgment of the investigator affect assessments of the clinical status to a significant degree and require discontinuation of protocol therapy. Note: Diagnosis of another neoplastic disease (second malignant tumour) does not mandate a stop of trial therapy, patients may continue to receive protocol treatment after appearance of a second primary tumour, stopping protocol treatment is determined by the medical judgment of the treating physician.
- Request by the patient. Patients have the right to refuse further trial treatment at any time during the trial. Such patients will remain in the trial and will be transferred to the follow-up phase.
- If a patient refuses to have follow-up examinations and tests needed to determine whether the treatment is safe and effective.

The decision for discontinuation of protocol treatment of individual patients is taken by the treating physician based on his medical evaluation and taking into account the patient's individual situation.

The patient will be followed for survival irrespective of whether treatment is discontinued (required provisions outlined in section 19.3).

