### **19.3. Withdrawal of consent**

Patients have the right to withdraw consent for further trial participation at any time without having to specify the reason. The data recorded up to the timepoint of withdrawal will continue to be evaluated in the trial. The investigator should ask the patient for consent to continue to collect information on her/his disease and survival status.

It should be documented in both the medical records and in the eCRF, according to the instructions in the *STIMULI CRF completion guidelines*, if the patient accepts to be contacted for survival status despite withdrawing the trial consent. For the patient's safety, an end of treatment visit should be performed and documented in the eCRF.

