2.2 Study's endpoints

2.2.1 Primary endpoint

The primary endpoint of the analysis is PFS, defined as the time from the **date of randomization** until documented progression (based on RECIST 1.1 criteria) or death, if progression is not documented. Censoring (patients without progression/death) for PFS will occur at the last tumour assessment. In the frame of a sensitivity analysis, if the last tumour assessment is «Non evaluable», censoring will occur to the more recent tumour assessment where an overall evaluable result is recorded.

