Data will be primarily analysed using the SAS software package (version 9.4), while the R statistical software will be also used for specific analysis and plots.

All analysis and reviews will be performed according to the Standard Operating Procedures (SOPs) of FSFH statistical team for the final analysis. A second statistician, the reviewing statistician, will independently reproduce all analysis and summary statistics. The reviewing statistician will have an overview of the entire analysis and will explicitly check the code producing tables and figures, as well as any other pieces of code as desired.

Data retrieval information

The final analysis will be based on the database download, that will take place, as soon as the total number of 81 PFS events required according to the statistical design of the trial are observed. Using this database extraction, a set of queries will be produced and forwarded to trial's data manager with the expectation to be answered in a pre-specified time period (approximately four weeks). Corrections and responses based on these queries, will be used for correcting the previously downloaded database, in order to create the final clean dataset to be used for the analysis.

Missing data

- Baseline characteristics

For categorical baseline characteristics if missing cases exist, a separate category named "Missing" will be created. As far as continuous values, missing cases will not be replaced by any statistics calculated over non-missing data.

- Dates:

If the day of the month is missing for any date used in the analysis, the 15th of the month will be used to replace the missing date unless the calculation results in a negative time duration (eg, date of onset cannot be prior to day one date). In this case, the date resulting in one day of duration will be used. If the day of the month and the month are missing for any date used in a calculation, i.e., January 1 will be used to replace the missing date. Missing dates for adverse events will be imputed based on the similar principle.

- Incomplete tumour assessment information

In patients who have no on-study assessments:

 If death is recorded prior to the first planned tumour assessment, the death date will be considered as the date of the PFS event.

- If clinical progression is recorded prior to the first planned tumour assessment, the date of the reported clinical progression will be considered as the date of the PFS event.

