- o In all other cases, the patient will be censored at the date of randomization plus 1 day.

Reporting conventions

Regarding the estimates presented in the report, the following rules will be adopted:

- P-values ≥0.001 will be reported with three decimal places
- P-values >0.010 will be reported with two significant demical digits
- P-values less than 0.001 will be reported as "<0.001"
- Means, medians, 95% confidence limits (Cis), quantiles, and any other summary statistics, will be reported with one decimal digit
- Hazard ratios (HRs) and their 95% CI's will be reported to two decimals
- Estimated parameters, not on the same scale as raw observations (e.g. regression coefficients) will be reported to three significant figures.

Multiple recordings of an event for the same patient

There are some cases where a patient may experience the same event (AE/SAE) more than once. In such cases, the event will be counted only once for the calculation of the total number of events reported for the overall safety cohort.

Presentation of results

The results will be presented through tables and figures. A summary of the results will also accompany the main report. First, a short synopsis of the results will be presented through bullets, where only the most important findings will be shown. Following that, a more detailed description of the results will be provided, sectioned in the following order:

- Patient accrual and baseline characteristics
- Follow-up and Treatment administration

- Efficacy analysis
- Safety analysis

All tables and figures will be included in an appendix.

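### SAP section 5 censors at day 1 a never-scanned patient who dies after the first planned scan, although SAP 2.2.1 and Protocol 14.1 count that death as a PFS event

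*SAP*

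**What the plan says.** SAP 2.2.1 defines PFS from randomisation to documented RECIST 1.1 progression "or death, if progression is not documented". It censors only patients with neither event: "Censoring (patients without progression/death) for PFS will occur at the last tumour assessment". Protocol 14.1 has the same event clause and a stricter censoring clause: "Censoring will occur at the last tumour assessment only if patient is lost to follow-up". Neither section limits when the death must occur or asks for an earlier scan.

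SAP section 5, under missing data, has a separate rule for patients with no on-study assessment. It has three branches:

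- "If death is recorded prior to the first planned tumour assessment, the death date will be considered as the date of the PFS event".
- Clinical progression recorded before that assessment is an event on its reported date.
- "In all other cases, the patient will be censored at the date of randomization plus 1 day".

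The first planned scan after randomisation is at week 9, with a window of one week either side, in both arms (Protocol 13.2). The final analysis is triggered by 81 PFS events (SAP 2.1) and uses the intention-to-treat cohort, which includes randomised patients who received no trial treatment (SAP 2.3).

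**The concern.** The third branch of section 5 takes in deaths that the endpoint definition counts. A patient with no post-randomisation scan and no clinical progression before week 9, who then dies with the death on record, moves from an event to one day of censored follow-up.

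This is not a general missed-scan convention. Under SAP 2.2.1, a patient with one non-progressing scan at week 9 who dies much later without another scan is still an event. Section 5 is not labelled a sensitivity analysis, and the SAP does not say which section prevails. The analyst and the reviewing statistician could code it differently.

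Such patients can exist in either arm. Protocol 19.2 foresees patients who refuse follow-up tests, yet "The patient will be followed for survival irrespective of whether treatment is discontinued". Protocol 19.3 has sites record "if the patient accepts to be contacted for survival status despite withdrawing the trial consent".

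At stake is the only primary endpoint. Neither planned PFS sensitivity analysis restores these deaths: one moves the censoring date when the last scan is non-evaluable (SAP 2.2.1), and the other changes the start date (SAP 4.5). The 81-event trigger can also be counted in two ways.

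**Working it through.** **1. The two rules applied to the same patients** (none scanned after randomisation; first planned scan at week 9).

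| Patient | SAP section 5 | SAP 2.2.1 / Protocol 14.1 |
|---|---|---|
| Dies week 5 | Event, week 5 | Event, week 5 |
| Dies week 8.9 | Event, week 8.9 | Event, week 8.9 |
| Dies week 12, no earlier clinical progression | Censored, day 1 | Event, week 12 |
| Dies week 20, no earlier clinical progression | Censored, day 1 | Event, week 20 |
| Dies week 40, no earlier clinical progression | Censored, day 1 | Event, week 40 |
| Clinical progression week 6, dies week 20 | Event, week 6 | Event |

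The conflict is confined to rows 3 to 5.

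**2. The plan's own figure.** Inputs from SAP 1.4 and section 3: one-sided alpha 0.05, power 80%, 1:1 allocation, medians 22.8 and 13.1 months, HR 0.57. Schoenfeld: d = 4(1.645 + 0.842)² / (ln HR)². With HR = 13.1/22.8 = 0.5746, d = 81, as stated; with HR rounded to 0.57, d = 79.

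**3. Power lost per death, none replaced.** Power = Φ(√d · |ln 0.57| / 2 − 1.645).

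- d = 81: Φ(2.530 − 1.645) = 81.2%
- d = 79: Φ(2.498 − 1.645) = 80.3%
- d = 77: Φ(2.466 − 1.645) = 79.4%

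Four lost deaths cost (81.2 − 79.4) = 1.8 points, or about 0.45 points each.

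**4. Effect on the test.** The documents give neither the number of affected patients nor the final number randomised, so both are assumed. Setup: 20,000 simulated trials per scenario, 1:1, uniform accrual over 40 months, exponential PFS with control median 13.1 months, cut at the 81st event by the definition. Then 2 or 4 events between week 9 and month 12 were recoded as censored at day 1. Results for 160 randomised, one-sided 5% log-rank, with the mean estimated HR in brackets:

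| True HR | Lost deaths | At random | All experimental | All observation |
|---|---|---|---|---|
| 1.00 (definition: 4.8%) | 2 | 4.9% | 6.7% (0.967) | 3.6% (1.036) |
| 1.00 | 4 | 5.0% | 9.2% (0.932) | 2.7% (1.075) |
| 0.57 (definition: 80.8%) | 2 | 80.2% | not shown | not shown |
| 0.57 | 4 | 79.6% | 89.0% (0.510) | 71.0% (0.603) |

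Results for 120 and 200 randomised agree within 0.4 points.

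**5. The scan window.** If the planned assessment means week 9 exactly, a patient who dies in week 9–10 with the scan still due is censored at day 1 without having missed anything. With exponential survival at the design OS medians, the proportion dying in that week is exp(−λ·9 wk) − exp(−λ·10 wk), where λ = ln 2 / median:

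- median 20.7 months: 0.00716
- median 29.7 months: 0.00510

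With 80 per arm: 80 × 0.00716 + 80 × 0.00510 = 0.57 + 0.41 = 0.98 deaths per 160 randomised (0.7 to 1.2 for 120 to 200). This is a ceiling, because it includes patients already scanned or already progressed.

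**The case against.** The strongest reply is that few patients can be affected. The protocol requires restaging when treatment stops for reasons other than progression unless recently done, a CT at progression, prompt imaging on suspicion of metastases, and an end-of-treatment visit even after consent is withdrawn. A patient must miss every scan, pass week 9 without recorded clinical progression, and still have a known death. This stands, and it supports calling the number small.

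Among never-scanned patients who pass week 9 without recorded progression, the rule is also blind to outcome: later deaths and survivors are all censored at day 1. That is true within that group. Across all never-scanned patients, early deaths count and later ones do not, so removal still depends on when the patient dies. The proposed fix has its own cost: it may date an event long after an unseen progression, and event-free survivors still contribute one day. It is preferred because it follows the stated definition, not because it is free of bias.

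The one-sided scenarios are extremes. If losses fell to either arm with equal chance, all four would be experimental with probability 1/16, and both of two with probability 1/4. The trial is open-label, so equal non-scanning cannot be assumed, but no passage supports a one-sided pattern.

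Week 9–10 deaths can fairly be read as preceding a scan planned at week 9 plus or minus one week, so that route is conditional. Protocol 14.1's censoring clause is a weak standard, since taken literally it leaves no censoring for event-free patients still in follow-up. The conflict rests on the event clause, which both documents share. If the 81 events are counted under section 5, lost events are replaced and the main effect is on timing. None of this removes the mismatch.

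**Conclusion.** The concern holds. For a never-scanned patient with no clinical progression before the first planned scan, section 5 censors a later death that SAP 2.2.1 and Protocol 14.1 count, and nothing in either document reconciles them.

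The effect is probably small: about 0.45 points of power per lost death, and no material change in type I error if losses are balanced. It becomes noticeable only if several such deaths fall in one arm, and the direction is then unknown, since the bias favours the arm that loses more deaths. These sizes rest on assumed counts of 2 or 4 lost deaths, 120 to 200 randomised, exponential PFS, and a cut at 81 events by the definition. The deaths remain in OS, which is now secondary. It should be fixed, because it leaves the derivation of the sole primary endpoint, and its event trigger, open to two readings.

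**What to change.** - In SAP section 5, state that death from any cause without prior documented progression is a PFS event on the date of death, whether or not a scan was done. Limit day-1 censoring to patients with no on-study scan and no PFS event.
- Count the 81 events that trigger the analysis by the same rule.
- If the current rule is wanted, keep it as a named sensitivity analysis and report, by arm, how many patients it reclassifies.

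The cost is SAP wording and a few lines of derivation code. No new data are needed, and the 81-event requirement does not change.
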